7.8.2.1 General laboratory evaluation

Laboratory values will be compared to their reference ranges and frequency tables will be provided for the number of patients within and outside the reference range at baseline and the last measurement on treatment. Descriptive statistics will be provided by treatment group for baseline, on-treatment values and for changes from baseline based on normalised values, as well as on the basis of standardized values for parameters with an incomplete reference range (e.g. ALT).

Descriptive statistics will in addition be calculated for the change from baseline in haematocrit over time, including during the follow-up period. In particular, statistics will be provided for last-value on-treatment, follow-up, change from baseline from last on-treatment value and follow-up, and change from last on-treatment assessment to follow-up.

Frequency tables will summarise the number of patients with potentially clinically significant abnormalities as defined for the new XLAB macro (version 2.03) and the criteria for clinically significant abnormalities based on normalised laboratory values will be listed.

7.8.2.2 Elevated liver enzymes

Special attention will be paid to parameters characterising liver function. These include liver enzymes (alanine aminotransferase (ALT), aspartate aminotransferase (AST), alkaline phosphatase (AP)) and total bilirubin.

The frequency of the number of patients with AST/ALT elevations $\geq 3xULN$, $\geq 5xULN$, $\geq 10xULN$, and $\geq 20xULN$ will be displayed.

To support analyses of liver related adverse drug effects, patients with AST and/or ALT $\geq 3xULN$ with concomitant or subsequent TBILI $\geq 2xULN$ in a 30 day period after AST/ALT elevation are of special interest. The start of the 30 day time span is triggered by each liver enzyme elevation above the defined thresholds. Patients who fulfil one or two of the criteria for AST/ALT or total bilirubin elevations above and has no information available for the remaining parameter(s) at the same time-point or within the 30 day time window will not be listed under "ALT and/or AST $\geq 3xULN$ with Total Bilirubin $\geq 2xULN$ ".

Patients with elevations as defined above by ALT and/or AST, total bilirubin and AP combinations, will be summarised and stratified by Alkaline phosphatase $< 2xULN$ and $\geq 2xULN$.

Details on patients with elevated liver enzymes will be listed.

In addition to the standard '3-day-on-treatment approach' detailed above, all liver enzyme elevation with an onset date up to 30 days after the treatment stop will be analysed for further displays in Section 15 of the CTR.

7.8.2.3 Lipid parameters

Descriptive statistics will be shown over time for the treated set (LOCF and OC) including change from baseline and percent change from baseline. For each lipid parameter, separate ANCOVA models will be fitted on the treated set (OC) for both change from baseline at week 26 and percent change from baseline at week 26 as dependent variables. The models will include treatment and pre-existing insulin therapy as fixed effects, and baseline lipid, baseline HbA1c, baseline eGFR (CKD-EPI, creatinine) are linear covariates.

The residuals from the ANCOVA models will be checked for normality using a Q-Q plot and documented in Appendix 16.1.9.2.

7.8.2.4 Renal laboratory parameters

Creatinine and eGFR

All calculations for the grading of renal function will be based on the originally measured laboratory values and the ULNs given by the laboratory, not on normalised values with BI standard reference ranges.

The glomerular filtration rate will be first estimated according to the following CKD-EPI creatinine equation, and stored in the trial database:

$$\begin{aligned} \text{eGFR (ml/min/1.73 m}^2\text{)} &= 141 \times \min(\text{serum creatinine [umol/L]/88.4/k, 1})^a \\ &\quad \times \max(\text{serum creatinine [umol/L]/88.4/k, 1})^{-1.209} \\ &\quad \times 0.993^{\text{Age}} \times [1.018 \text{ if female}] \times [1.159 \text{ if of African origin}] \end{aligned}$$

Where:

- k is 0.7 for females and 0.9 for males,
- a is -0.329 for females and -0.411 for males,
- min indicates the minimum between (serum creatinine/k) and 1,
- max indicates the maximum between (serum creatinine/k) and 1.

For the analysis of eGFR (CKD-EPI, creatinine) and for the covariates in the efficacy statistical modelling the values calculated from the above formula using the serum creatinine values from the central laboratory will be used, and not the eGFR values provided by the central laboratory.

The glomerular filtration rate will also be derived according to the following CKD-EPI creatinine-cystatin C equation:

$$\begin{aligned} \text{eGFR (mL/min/1.73 m}^2\text{)} = & 135 \times \min(\text{serum creatinine [mg/dL]/ k, 1})^a \\ & \times \max(\text{serum creatinine [mg/dL]/ k, 1})^{-0.601} \\ & \times \min(\text{standardized serum cystatin C [mg/L]/0.8, 1})^{-0.375} \\ & \times \max(\text{standardized serum cystatin C [mg/L]/0.8, 1})^{-0.711} \\ & \times 0.995^{\text{Age}} \\ & \times 0.969 \text{ [if female]} \\ & \times 1.08 \text{ [if black]} \end{aligned}$$

Where:

- k is 0.7 for females and 0.9 for males,
- a is 0.248 for females and -0.207 for males,
- min (serum creatinine/ k, 1) indicates the minimum between (serum creatinine/k) and 1,
- max (serum creatinine/ k, 1) indicates the maximum between (serum creatinine/k) and 1,
- min (standardized serum cystatin C / 0.8, 1) indicates the minimum between (standardized serum cystatin C /0.8) and 1,
- max (standardized serum cystatin C / 0.8, 1) indicates the maximum between (standardized serum cystatin C /0.8) and 1
- Age is expressed in years.

The endpoint eGFR (CKD-EPI, creatinine-cystatin C) will be derived at the visits where both serum creatinine and serum cystatin C are measured at the central laboratory.

The following additional rules will apply to derive these two eGFR renal endpoints:

- In case of mixed race, if ‘Black or African American’ is one of the patient races, eGFR will be by default derived as if the patient is of African origin.
- Age will be considered as a discrete variable for the above calculations, and the age will be from the same visit as the other variables. The age at a specific visit where eGFR is calculated will be derived as follows:

age [years] = (date of eGFR laboratory measurement – birth date + 1) / 365.25

A shift table from baseline to last value on treatment, (and from baseline to minimum value on treatment) will be provided for eGFR (CKD-EPI, creatinine) and for eGFR (CKD-EPI, creatinine-cystatin C) endpoints.

Descriptive statistics will also be created for creatinine, eGFR (CKD-EPI, creatinine) and eGFR (CKD-EPI, creatinine-cystatin C) values over time by treatment and presented in tables.

Additionally, a summary will be created representing the number of patients per treatment group that experienced a doubling in creatinine on treatment that was out of the normal range as compared to baseline.

Other renal endpoints

The following renal endpoint will be analysed:

- Doubling of serum creatinine accompanied by eGFR (CKD-EPI, creatinine) ≤ 45 mL/min/1.73m². For this endpoint, the doubling of serum creatinine level corresponds to the increase of serum creatinine level to 2.0 fold from baseline.

Patients who already fulfil the above condition at baseline or without post-baseline laboratory measurements are not considered in the number of patients at risk for this endpoint. If a baseline laboratory measurement is not available for the parameter of interest, it is assumed that the patient did not experience the condition corresponding to the endpoint at baseline.

The number of patients with the event will be provided.

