- iPTH (intact parathyroid hormone)⁴
- Sodium
- $TSH^{1,5}$
- Blood urea nitrogen (BUN)
- Uric acid

Lipids⁶

- Cholesterol (total)
- HDL cholesterol
- LDL cholesterol (calculated)
- Free fatty acids

- Apo A-1
- Apo B
- **Triglycerides**
 - o direct measurement of LDL cholesterol (reflex test if triglycerides are > 400 mg/dL or 4.52 mmol/L)
- At the screening visit (Visit 1), only the following parameters are part of the profile: liver transaminases, alkaline phosphatase, creatinine, and TSH
- C-peptide will only be assessed at Visit 2
- Cystatin C will only be assessed at Visits 6, 11 EOT, eEOT (if applicable) and 12
- iPTH will be only be assessed at Visits 6, 8, 11 EOT and eEOT (if applicable)
- TSH will only be assessed at Visit 1
- Lipids will only be assessed at Visits 6, 11 EOT, eEOT (if applicable), and 12

Page 55 of 122

Proprietary confidential information © 2016 Boehringer Ingelheim International GmbH or one or more of its affiliated companies

Table 5.3.3: 2 Laboratory parameters – urine

Semi-quantitative (dipstick) urinalysis		Quantitative urinalysis		
•	Nitrite ¹	•	Albumin	
•	Protein	•	Creatinine	
•	Ketones ³	•	Human chorionic gonadotrophin	
•	Urine pH		$(hCG)^2$	
•	Leukocyte esterase (for WBC) ¹			

Microscopic urinalysis

Microscopic analysis will be performed as a reflex test if any of the above semiquantitative (dipstick) tests except for ketones are abnormal:

- Urine RBC/erythrocyte
- Urine WBC/leukocytes¹
- Urine sediment microscopic examination

Urine culture

Urine culture will be triggered by positive leukocyte esterase (for WBC) and/or nitrite in the semi-quantitative test/dipstick. The culture will include an antibiogram

- Nitrite and leukocyte esterase (for WBC) will be determined both locally on site (not recorded in eCRF) and via the central laboratory. A positive result at site triggers the sampling of mid-stream urine for urine culture
- Urine pregnancy testing will be performed locally in female patients of child-bearing potential only according to the timepoints indicated in the Flow Chart
- At clinic visits where centralized safety laboratory tests are not planned, urine ketones will be determined only locally at the site.

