7.1 DEMOGRAPHICS AND OTHER BASELINE CHARACTERISTICS

7.1.1 Baseline evaluation

Descriptive analysis of the following demographic variables measured at baseline will be presented:

Sex, race, ethnicity, region, age (years), age-groups, BMI (kg/m²) categories, height (cm), smoking history and alcohol status, time since diagnosis of diabetes (years) (continuous and in categories), eGFR by CKD-EPI creatinine equation (continuous and in categories) and eGFR by CKD-EPI creatinine-cystatin C (continuous and in categories).

See [Section 7.8.2.4](#) for details on the derivation of eGFR endpoints.

Descriptive analysis of the following variables measured at baseline will be presented:

HbA1c (%) (continuous and in categories), FPG (mg/dL) (continuous and in categories), weight (kg) (continuous and in categories), waist circumference (cm), blood pressure (mmHg) (continuous and in categories), UACR (mg/gcrea) (continuous and in categories), fasted serum BHB (mmol/L) (continuous and in categories), capillary daily patient self-measured BHB (mmol/L) (continuous and in categories) and capillary morning patient self-measured BHB (mmol/L) (continuous and in categories).

Baseline hypoglycaemia rates will be presented in a separate table, displaying both the rate (per 30 days) and the frequency (from day -28 to day -1, inclusive) of 'severe hypoglycaemia events confirmed by adjudication' and 'symptomatic hypoglycaemia AEs with confirmed plasma glucose <54mg/dL and/or severe hypoglycaemia events confirmed by adjudication'. For the rates, the statistics will include the number of patients overall (N), the number of patients with at least 1 event (Nh), mean, SD, SE, min, 5th percentile (P5), P10, P25, median, P75, P90, P95, and max.

[REDACTED]

Categories for baseline characteristics are defined in [Section 6.4](#).

Demographic and baseline characteristics tables will be presented on the FAS.

The demographic analysis will be repeated on the randomised population in Appendix 16.1.9.2 for disclosure on EudraCT.

[REDACTED]

[REDACTED]

[REDACTED]

- [REDACTED]
- [REDACTED]
- [REDACTED]
- [REDACTED]
- [REDACTED]
- [REDACTED]

[REDACTED]

[REDACTED]

[REDACTED]

[REDACTED]

[REDACTED]

[REDACTED]

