7.8.2 Laboratory data

For continuous safety laboratory parameters standardised and normalised values will be derived as well as the differences to baseline. The process of standardisation and normalisation as well as standard analyses for safety laboratory data are described in the BI guidance for the Display and Analysis of Laboratory Data (10). All analyses considering multiple of times upper limit of normal (ULN) will be based on original and not normalized data.

The analyses of laboratory data will be descriptive in nature and will be based on BI standards.

Results of laboratory analyses will be presented based on both SI units and US conventional units.

Baseline for safety laboratory parameters will be the last available measurement before the start of randomised study drug. In general, laboratory measurements taken up to 3 days after the last administration of randomised study drug will be considered as on-treatment. The exception will be for the liver enzyme elevation analysis (see below).

Only patients with at least one available on-treatment value will be included in the analysis of an individual laboratory parameter. All individual data will be presented in listings.

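### The creatinine-cystatin C eGFR formula has a positive creatinine exponent for women, so it understates eGFR below 0.7 mg/dL and reverses or dampens a creatinine-driven fall

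*SAP*

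**What the plan says.** SAP section 7.8.2.4 gives two eGFR equations. For the creatinine-only equation, the exponent that applies when creatinine is below k is stated as "a is -0.329 for females and -0.411 for males". For the creatinine-cystatin C equation it is stated as "a is 0.248 for females and -0.207 for males". In both, k is 0.7 mg/dL for women and 0.9 mg/dL for men.

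The second eGFR is used in three places:

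- Baseline (SAP 7.1.1): "eGFR by CKD-EPI creatinine-cystatin C (continuous and in categories").
- Over time (SAP 7.8.2.4): "Descriptive statistics will also be created for creatinine, eGFR (CKD-EPI, creatinine) and eGFR (CKD-EPI, creatinine-cystatin C) values over time".
- Shift tables (SAP 7.8.2.4), for both versions of eGFR: "A shift table from baseline to last value on treatment, (and from baseline to minimum value on treatment) will be provided for eGFR".

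The SAP assigns the first equation to the modelling: "For the analysis of eGFR (CKD-EPI, creatinine) and for the covariates in the efficacy statistical modelling" the creatinine-only values are used. The protocol limits when the second eGFR can exist (section 5.3.3, Table 5.3.3: 1): "Cystatin C will only be assessed at Visits 6, 11 EOT, eEOT (if applicable) and 12".

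**The concern.** The section's two equations contain eight creatinine and cystatin C exponents. Seven are negative: -0.329, -0.411 and -1.209 in the first, and -0.207, -0.601, -0.375 and -0.711 in the second. Only the female creatinine exponent in the second is positive. It conflicts with the male value beside it, with the same equation above k, and with the female term of the creatinine-only equation. No other visible text corrects it.

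A programmer who follows the SAP would therefore compute wrong values for women with creatinine below 0.7 mg/dL. The error depends on each woman's creatinine, so it does not cancel in a change from baseline. Direction of change is what these tables are meant to show: protocol section 1.2.3.1 describes a reduction in eGFR on empagliflozin in type 2 diabetes that reversed when the drug was stopped. In the affected women this endpoint could move the opposite way from the creatinine-only eGFR tabulated beside it.

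**Working it through.** The plan gives no worked eGFR value to reproduce, so the printed equation was evaluated directly.

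**Inputs (SAP 7.8.2.4), for a woman not recorded as black.** With Cr in mg/dL and Cys in mg/L:

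eGFR = 135 × min(Cr/0.7, 1)^a × max(Cr/0.7, 1)^-0.601 × min(Cys/0.8, 1)^-0.375 × max(Cys/0.8, 1)^-0.711 × 0.995^age × 0.969

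Printed: a = +0.248. Comparison: a = -0.248 (sign changed, size kept; an assumption). For illustration: age 45, Cys 0.9.

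**1. Error in level.** The exponent a acts only when Cr < 0.7. All other terms cancel in the ratio:

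printed / negative = (Cr/0.7)^(0.248 + 0.248) = (Cr/0.7)^0.496

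This holds at any age, race or cystatin C. For the example, the remaining factors are 135 × 0.995^45 × 0.969 × (0.9/0.8)^-0.711 = 104.4 × 0.920 = 96.0.

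| Cr (mg/dL) | Printed | With -0.248 | Error |
|---|---|---|---|
| 0.4 | 83.6 | 110.3 | -24% |
| 0.5 | 88.3 | 104.4 | -15% |
| 0.6 | 92.4 | 99.8 | -7% |
| 0.7 | 96.0 | 96.0 | 0 |

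**2. Change in creatinine, cystatin C unchanged.**

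- 0.5 to 0.7: printed 1.4^0.248 - 1 = +8.7%; negative 1.4^-0.248 - 1 = -8.0%. The fall is reversed.
- 0.5 to 0.8: +0.3% against -15.1%. The fall disappears.
- 0.6 to 0.8: -4.1% against -11.2%. The fall is dampened.

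The printed formula shows a rise until creatinine reaches 0.7 × (Cr0/0.7)^(-0.248/0.601), where Cr0 is the starting value: about 0.75 from 0.6 and about 0.80 from 0.5.

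**3. Both markers rising** (Cys from 0.8 or above, Cr staying at or below 0.7). If Cr is multiplied by r, the printed formula still shows a rise only if Cys rises by less than r^(0.248/0.711) - 1:

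- r = 1.4: 12.5%
- r = 1.1: 3.4%

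If both rise by the same factor r, the printed change is r^(0.248 - 0.711) - 1 and the comparison is r^(-0.248 - 0.711) - 1:

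- both +10%: -4.3% against -8.7%
- both +40%: -14.4% against -27.6%

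**4. If the true size is not 0.248.** For a true exponent of -x, the level error is (Cr/0.7)^(0.248 + x) - 1. For x from 0.15 to 0.40 this is -12.5% to -19.6% at 0.5 mg/dL, and -6.0% to -9.5% at 0.6 mg/dL.

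**5. Possible group effect.** The documents do not give the share of women below 0.7 mg/dL. The shift in the female mean is share × (printed - negative), using -7.3 mL/min/1.73 m² at 0.6 and -16.0 at 0.5 from step 1:

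| Assumed share | All at 0.6 | All at 0.5 |
|---|---|---|
| 10% | -0.7 | -1.6 |
| 30% | -2.2 | -4.8 |
| 50% | -3.7 | -8.0 |

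**6. Reach in time.** SAP 7.8.2 states that "laboratory measurements taken up to 3 days after the last administration of randomised study drug will be considered as on-treatment". Visit 12 falls three weeks after treatment ends, so it lies outside that window. Most patients have one scheduled on-treatment value, at Visit 11 EOT or at eEOT.

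**The case against.** The strongest counter-argument is that the minus sign may have been lost when the PDF was converted to text. The converted SAP is not a perfect copy: its contents list runs from 5.2.3 to 5.2.100, all on page 11, with no matching sections in the body. Against this, the minus sign survives on the male value in the same line and on both values in the parallel creatinine-only line. A lost character is unlikely but not excluded, because the page image was not seen.

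Second, the documents show an inconsistent sign, not the correct value. That stands, and step 4 gives the range for this reason. The documents also cannot confirm the sizes of the other coefficients.

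Third, the group shifts rest on assumed shares and creatinine values. The renal tables are planned by treatment, and no by-sex table is visible, so men would dilute any shift. That stands too: step 5 shows what the error could do, not what to expect.

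Fourth, the consequence is limited. The outputs are descriptive, creatinine and creatinine-only eGFR are tabulated alongside, and the SAP names the equation, so a programmer could take it correctly from its source. This bears on severity. It does not make the written rule right, and nothing in the documents shows that the program departs from it.

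**Conclusion.** The concern holds. The female exponent in the creatinine-cystatin C equation has the wrong sign by the SAP's own pattern, and following the text gives wrong values for women with creatinine below 0.7 mg/dL. The direction of the error does not depend on the assumed size of the exponent; the exact percentages do. When cystatin C rises materially as well, the fall is understated rather than reversed.

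Not affected are men, women at or above 0.7 mg/dL, the efficacy covariates, creatinine-only eGFR, the creatinine-based adverse event of special interest and the doubling-of-creatinine endpoint. The category cut-offs are not visible, so no misclassification in the shift tables is claimed. The correction should be made because it is cheap and the tables report safety, but it does not threaten the trial's main conclusions.

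**What to change.** Check the original page of SAP section 7.8.2.4. If it prints a positive value, make the female exponent in the creatinine-cystatin C equation negative (-0.248), with the size confirmed against the source equation. In either case, before database lock, compare the derivation program with a hand calculation for one woman with creatinine below 0.7 mg/dL. With the SAP's other coefficients, age 45, creatinine 0.5 mg/dL and cystatin C 0.9 mg/L should give 104.4 if -0.248 is confirmed; 88.3 would show that the positive exponent was programmed. Nothing in this point requires a change to the creatinine-only equation, whose exponents are consistent in sign.

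The cost is one character in the SAP, one look-up and one program check.

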7.8.2.5 Blood beta-hydroxybutyrate (BHB)

Refer to [Section 6.7](#) for the baseline definition of BHB endpoints.

- Serum BHB sampled at the site and analysed at the central laboratory

All the analyses described for this endpoint will be performed on fasted measurements only.

Descriptive statistics for baseline, actual values and change from baseline over time will be calculated. Descriptive statistics will also be provided to characterize the follow-up period.

The median and the corresponding confidence interval using SD will be plotted over time including the follow-up period. A box-plot presenting the value at baseline and over time will also be produced per treatment group.

A shift table from baseline to last value on treatment, (and from baseline to maximum value on-treatment) will also be provided by baseline values (<0.6 mmol/L, 0.6 to ≤ 1.5 mmol/L, >1.5 to <3.8 mmol/L, ≥ 3.8 to ≤ 8.0 mmol/L, > 8.0 mmol/L).

An additional shift table will display the number of patients in these BHB categories over time.

- Capillary self-measured BHB via the ketone meter and reported in the diary

Elevated ketone readings above >1.5 mmol/L that have not been confirmed by the investigator will not be included in any analysis of this section. Refer to [Section 5.4.6.1](#) for further details on the ketone reading confirmation process.

Morning and daily endpoints

For all analyses specified in this section, capillary BHB readings reported as “HI” will be imputed to 8.1 mmol/L.

The periods of time of interest will be the following ones: week 1, week 2, week 3, week 4, week 5 to week 6, week 7 to week 8, week 12, week 18, week 22 and week 26.

Descriptive statistics will be produced on the average of morning BHB measurement values over the specific periods of time defined above.

The same descriptive statistics will be produced on the average of daily BHB measurement values over time, using the same periods of time defined above.

High BHB measurements

The analysis described in this paragraph will focus on high BHB measurement values that a patient may have reported in the diary. For this analysis, "HI" readings will be considered as such and not be replaced by a numerical value (for instance 8.1 mmol/L).

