advised to reduce the patient's total insulin dose based on need/ by 10% to minimise the risk for hypoglycaemia. Since glomerular filtration is physiologically decreased during episodes of severe hypoglycaemia (due to reduced renal blood flow hence leading to lowering of urine glucose excretion and therefore efficacy of empagliflozin), hypoglycaemia induced by insulin is not expected to be significantly aggravated by empagliflozin [R12-4766].

Special attention will be paid to prevent T1DM-inherent DKA. Due to the mechanism of action, empagliflozin may potentially modify the clinical presentation of DKA. Patients receiving empagliflozin may be at risk to underestimate their need for insulin if blood sugar levels are within individual target ranges or only slightly elevated. Insulin deficiency might lead to ketoacidosis which could be life-threatening if not recognised and appropriately treated. All patients will be made aware of this risk and be instructed not to reduce their insulin dose below Investigator recommendations. In addition to blood glucose monitoring, the frequency of which will be increased after starting the study medication (for further details see Section 5.3.2.1), in the same way as during routine clinical care, patients will be reminded how to determine ketones in case of any symptoms of DKA, e.g. nausea, vomiting, abdominal pain etc. They will be instructed to do this irrespective of the glucose value in the event of DKA symptoms occurring. More frequent ketone testing (e.g. once daily) will be recommended during the run-in period and during the first 4 weeks of the treatment period; this will allow patients and Investigators to understand baseline ketosis rates and compare them, as appropriate, to the incidence of ketosis following the initiation of study medication. A meter will be provided to the patient for this purpose; as an additional safeguard, the meter will also be used to check ketone levels at most clinic visits (see Flow Chart). Patients will be reminded of the interpretation of ketone values measured by the meter, and on appropriate action to be taken in the event of increased ketone levels (see Section 5.3.2.2). In addition, patients will be reminded about insulin adjustment during "sick days" and about the importance of keeping themselves hydrated.

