5.3.3 Safety laboratory parameters

At the following visits, laboratory samples will be collected from the patient after a full overnight fast (i.e. nothing to eat or drink except water for at least 10 hours): Visits 2, 6, 9, 11 EOT, eEOT (if applicable), and 12. At all other visits, the patient does not have to be in a fasted state when laboratory samples are taken.

When applicable, laboratory samples, as described in the Flow Chart, should be collected before trial medication is taken.

All parameters that will be determined during the trial conduct are listed in Table 5.3.3: 1 and Table 5.3.3: 2. The analysis will be performed by a central laboratory. The respective reference ranges and details about sample handling and shipment will be provided in the laboratory manual in the ISF.

UACR in spot urine will be calculated at the central laboratory.

The central laboratory will derive the eGFR from (and report it together with) serum creatinine values based on the CKD-EPI formula which is considered more accurate in the normal range than the Modification of Diet in Renal Disease (MDRD) formula. The CKD-EPI formula will be defined in central laboratory documentation due to regional/racial variations in the formula that is applied.

The eGFR (cystatin C, serum) will also be derived, at the visits where cystatin C levels are measured.

Page 54 of 122 Proprietary confidential information © 2016 Boehringer Ingelheim International GmbH or one or more of its affiliated companies

Table 5.3.3: 1 Safety laboratory parameters – blood, serum or plasma

Haematology

- Haematocrit
- Haemoglobin
 - reticulocyte count (reflex test if haemoglobin is outside normal range)
- Red blood cells (RBC)/erythrocytes
- White blood cells (WBC)/leukocytes
- Platelet count/thrombocytes
- Differential automatic (relative and absolute count):
 - neutrophils, eosinophils, basophils, monocytes, lymphocytes

Clinical chemistry

- Albumin
- Alkaline phosphatase¹
 - gamma-glutamyl transferase (γ-GT, reflex test triggered by elevated alkaline phosphatase on two sequential measures)
- ALT (alanine aminotransferase, SGPT)¹
- AST (aspartate aminotransferase, SGOT)¹
- Beta-hydroxy-butyrate
- Bicarbonate
- Bilirubin total, fractionated if elevated
- Calcium
- Chloride
- C-peptide²
- Creatinine¹

- Creatine kinase (CK)
 - o troponin I (reflex test if CK is elevated)
- Cystatin C³
- Lactate dehydrogenase
- Lipase
- Magnesium
- Phosphate
- Potassium
- Protein total

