6.2.2.2 Interim visits (Visits 7-10)

- Visit 9 should be done with the patient in a fasted state (i.e. no food or drink except water for 10 hours); Visits 7, 8 and 10 do not require fasting
- Prior to each clinic visit, patients should be reminded to attend without having taken their trial medication in the morning, and to bring all used/unused medication with them to the visit
- using their SBGM device, starting directly before a dose of study medication is administered, and to continue this until directly before administering study medication on the following day

Proprietary confidential information © 2016 Boehringer Ingelheim International GmbH or one or more of its affiliated companies

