7.8.2.6 Urine ketone

Refer to [Section 6.7](#) for the baseline definition of urine ketone endpoints.

The analyses described for this endpoint will be performed on fasted measurements only.

Analysis of categorical urine ketone data (negative, trace, 1+/small, 2+/moderate, 3+/large, 4+/large+) will be performed by value at baseline, over time, and worst value on treatment. The analysis will be presented as frequency table and graphically on pie charts.

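### The fasted-only rule for the serum BHB shift to maximum and the worst urine ketone leaves out the scheduled Week 4 sample, so both tables can only understate the extreme value

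*SAP*

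**What the plan says.** SAP 7.8.2.5 deals first with serum BHB sampled at the site and measured centrally. It opens with a blanket restriction: "All the analyses described for this endpoint will be performed on fasted measurements only". The outputs listed under it include descriptive statistics over time, plots, and a shift table by BHB category that runs to the last on-treatment value and also "from baseline to maximum value on-treatment".

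SAP 7.8.2.6 does the same for urine ketones: "The analyses described for this endpoint will be performed on fasted measurements only". The categorical analysis is then specified "by value at baseline, over time, and worst value on treatment".

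Protocol 5.3.3 lists the visits with fasted laboratory samples: "Visits 2, 6, 9, 11 EOT, eEOT (if applicable), and 12". Protocol 6.2.2.2 says of the interim visits that "Visits 7, 8 and 10 do not require fasting". These three are Weeks 1, 4 and 18.

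**The concern.** A fasted-only rule suits means and medians by visit, because SAP 6.7 defines baseline serum BHB as the fasted Visit 6 value and like is then compared with like. A maximum or worst-value table has a different purpose: it should search every on-treatment value for the most extreme one. If a non-fasted Week 4 sample shows a high BHB or a strongly positive urine ketone, the rule keeps it out of the table whose label says it should be there.

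The timing adds weight. The protocol asks for special caution at the start of treatment (4.2.1). It recommends more frequent home ketone testing in the run-in and the first 4 weeks, so that patients and investigators can take baseline ketosis rates and "compare them, as appropriate, to the incidence of ketosis following the initiation of study medication" (2.3). That sentence concerns home testing and sets no requirement for the laboratory tables, but it shows which weeks the sponsor regards as important for ketosis.

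**Working it through.** There is no sample size, power or alpha figure to reproduce. The check crosses the sampling schedule with fasting status. The schedule and fasting columns come from the protocol Flow Chart, and Table 5.3.3: 1 lists BHB within the safety laboratory.

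| Visit | Fasting visit | Central safety laboratory and urinalysis | Site blood and urine ketone |
|---|---|---|---|
| 7 (Week 1, Day 8) | no | no | yes |
| 8 (Week 4, Day 29) | no | yes | yes |
| 9 (Week 12, Day 85) | yes | yes | yes |
| 10 (Week 18, Day 127) | no | no | yes |
| 11 EOT (Week 26, Day 183) | yes | yes | yes |
| eEOT (early stoppers only) | yes | yes | yes |

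**Serum BHB.** Scheduled on treatment: Weeks 4, 12 and 26, so 3 samples. Fasted: Weeks 12 and 26, so 2. Lost: 3 − 2 = 1, the Week 4 sample, or 1/3 = 33%. Serum is not drawn at Weeks 1 or 18, so nothing is lost there.

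**Urine ketone.** The count depends on a point the documents leave open. A footnote to Table 5.3.3: 2 says that at visits without central safety laboratory tests, urine ketones are tested at the site only. That describes Weeks 1 and 18, and nothing says whether those results reach the analysis database.
- Central results only: Weeks 4, 12 and 26 are scheduled and Weeks 12 and 26 are fasted, so 1 of 3 is lost (33%).
- Site results also recorded: Weeks 1, 4, 12, 18 and 26 are scheduled and Weeks 12 and 26 are fasted, so 3 of 5 are lost (60%).

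**First eligible value.** For a patient who stays on treatment, the first scheduled fasted sample is on Day 85. That is 85 − 1 = 84 days, or 12 weeks, after Day 1.

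**Early stoppers.** The eEOT visit is fasted (Protocol 6.2.3.2) and its measurements go into the visit window where they fall (SAP 6.7, Table 6.7: 2, footnote A), so such a sample can enter before Week 12. Laboratory values count as on treatment only up to 3 days after the last dose (SAP 7.8.2), while the example in Protocol 6.2.3.2 places eEOT a week after stopping. A patient who stopped at Week 6 on that pattern would have a Week 4 BHB but no scheduled fasted on-treatment value for the shift table.

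**Direction.** Write x4, x12 and x26 for a patient's three serum values. The fasted-only maximum is max(x12, x26) and the full maximum is max(x4, x12, x26). The first can never exceed the second, and they differ exactly when x4 is larger than both others. The table changes only if the two maxima fall in different SAP categories. As a hypothetical case, a Week 4 value of 4 mmol/L with both later values below 0.6 would be shown in the lowest category instead of the 3.8 to 8.0 category. The same reasoning holds for the worst urine grade.

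**Number of patients.** The documents give no rate of elevated values by visit and no within-patient correlation, so the number of patients misplaced cannot be calculated.

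**The case against.** The strongest reply is that early ketone safety is covered elsewhere, and much of this stands.
- Capillary self-measured BHB is summarised for each of Weeks 1 to 4, then Weeks 5 to 6 and 7 to 8, with a separate analysis of high diary values (SAP 7.8.2.5).
- The ketosis endpoints accept serum or capillary readings with no stated fasting limit, and adjudicated ketoacidosis is analysed by time to onset (SAP 7.8.1.4).
- SAP 6.6.2 plans the minimum and maximum post-baseline value for quantitative safety laboratory variables, with no fasting limit.

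A reader might therefore infer that the plan overlooks ketosis in the early weeks. The documents do not support that reading. What remains is narrower: none of these outputs gives the categorised shift to maximum serum BHB or the worst urine ketone. The weekly capillary summaries are averages, and the capillary section excludes readings above 1.5 mmol/L that the investigator has not confirmed. If SAP 6.6.2 is applied to BHB, the report could also carry two different maxima for the same parameter.

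It can also be said that the rule is openly stated, is applied to every arm in descriptive tables, and matches the fasted baseline. That is a good reason to keep a fasted-only version, but not to make it the only one. The protocol does say that drug-related ketone rises occur especially in the fasted state (2.3 and 5.3.2.2). Non-fasted values may therefore run lower, which would shrink the loss. By the same reasoning, a high non-fasted value is harder to put down to that effect.

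Finally, a visit that does not require fasting does not forbid it, and visits take place in the morning. The SAP does not say whether fasted means actual or scheduled status. If it means actual status, some Week 4 samples would qualify.

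**Conclusion.** The point holds for two descriptive safety tables. For patients who remain on treatment, the serum BHB shift to maximum loses 1 of 3 scheduled samples (Week 4). The worst urine ketone loses Week 4, and Weeks 1 and 18 as well if site results are recorded. The first scheduled fasted input is Week 12. The effect has one direction: these tables can understate the extreme but cannot overstate it.

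Three stronger readings should be resisted. The tables do not strictly begin at Week 12, because a fasted eEOT sample can come earlier. A urine loss of 3 of 5 is not established, because the Week 1 and Week 18 tests are local. The fasted-only rule is not unsound in general; it is reasonable for by-visit summaries.

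The conclusion assumes that fasted status follows the schedule, or that patients were in fact not fasted at Week 4. No confirmatory test is affected.

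**What to change.** In SAP 7.8.2.5 and 7.8.2.6:
- Keep the fasted-only restriction for by-visit means, medians, plots and over-time tables.
- Produce the shift from baseline to maximum on-treatment serum BHB, and the worst on-treatment urine ketone, from all recorded on-treatment measurements regardless of fasting status. Show the fasted-only version alongside, labelled as such.
- State whether fasted means the patient's actual status at sampling or the scheduled status of the visit.
- State whether the site-only urine ketone results of Weeks 1 and 18 are recorded and enter the analysis.

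The cost is a few sentences in two SAP sections and one extra version of each of two tables. No new sampling is needed. The drawback is that some maxima will be non-fasted values set against a fasted baseline, which the paired presentation makes visible.
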